### Timeline

9:00am – Arrival, snack, breath and urine tests  
9:15am – Mood (POMS), drug effect (DEQ) and cardiovascular measures  
9:30am – Tablet administered  
10:00am - Mood (POMS), drug effect (DEQ) and cardiovascular measures  
10:30am - Mood (POMS), drug effect (DEQ) and cardiovascular measures  
10:45am – Social Choice Task, Psychophysiology sensors applied  
11:00am – IAPS, ABT, social feedback, social touch task counterbalanced  
12:30pm –Mood (POMS), drug effect (DEQ) and cardiovascular measures  
1:00pm - Mood (POMS), drug effect (DEQ) and cardiovascular measures  
1:15pm – Leave Laboratory

**Debriefing:** Participants will be emailed a final DEQ rating of how much they liked each study drug and how much they would want to take each study session drug again. Participants will also be asked to report which type or types of drugs they think they received at each session. Finally, participants will be fully debriefed with regard to the study hypotheses, methods and the types of drugs that they received, and will be given a chance to ask any final questions in person, via phone, or via email.

### Data Analysis

The subjective effects of the drug will be assessed using three-way repeated measures analysis of variance (ANOVA), with group (high vs. low BDI scores) as the between-group factor and dose and time as within-subjects factors. We hypothesize buprenorphine will dose-dependently reduce depressed mood in those individuals with high scores on the BDI. Our primary mood measure will be scores on the Depression scale of the POMS.

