**Subjects:** 86 healthy volunteers (18 male, 18 female; age range 18-35 years) will participate in the experiment. Based on our previous rates of participants completing two-session drug studies, to recruit 86 complete subjects we will need to consent 120 participants. Participants with a range of scores on the Beck Depression Inventory (BDI-II; Beck et al., 1996) and State-Trait Anxiety Inventory (STAI; Spielberger et al. 1983) will participate in the experiment. The BDI-II contains 21 questions, each scored from 0 to 3. Higher total scores indicate more severe depressive symptoms. The standardized cutoffs are: 0–13: minimal depression, 14–19: mild depression, 20–28: moderate depression and 29–63: severe depression. We will aim to recruit approximately half the participants in the 0–13 range, and half in the 14–28 range. Candidates who meet criteria for Major Depressive Disorder will be excluded and referred for treatment. All participants will be recruited without regard to race, religion or ethnicity through posters, advertisements and word-of-mouth referrals. Candidates will be screened in accordance with our general screening protocol, approved by the IRB under Protocol #13681B, which includes a physical, EKG, psychiatric screening interview and detailed drug use history questionnaire. Because buprenorphine will be administered as part of the study, the following populations are excluded for safety reasons: Individuals with a medical condition contraindicating study participation, as determined by our physician (e.g. liver or kidney disease), individuals regularly using any contraindicated medications (e.g. opioid pain-killers), individuals with current or past opioid abuse or dependence, individuals with past dependence on other drugs, individuals with a DSM-IV Axis I mood, anxiety, eating, or psychotic disorder, individuals with a previous bad reaction to buprenorphine, women who are pregnant, nursing, or planning to become pregnant in the next 3 months. The self-report questionnaires we use require fluency in English, and have not been translated and validated in other languages, thus individuals with less than a high-school education or those not fluent in English will be excluded, as lack of English familiarity at a high school level may compromise our ability to interpret their self-reports. Individuals with a BMI below 19 or above 30 will also be excluded, as this would change dosing requirements.

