Study Session: Please see below for a full timeline of the study session. On study session days, participants will arrive at 1pm, and consume a standardized snack. Participants will then complete a urine and breath screening for recent alcohol and drug use, and a pregnancy test (for women). We will then take Time 1 measures of subjective mood, drug effects and cardiovascular variables. We will continue to take these same measures periodically throughout the study (see below). Participants will be administered the drug or placebo at 1:30pm. While waiting for the drug effect to reach peak, participants will be allowed to relax and watch a movie or read a book, but will not be allowed to do work. At 2:pm and 2:30pm we will reassess mood. The task portion of the study will begin 1.5 hrs after administration of the drug, and will last for approximately 1.5 hours, to coincide with the peak effect of the drug. Participants will first have the areas for the psychophysiological electrodes for EMG and EOG prepped by cleaning with a rubbing alcohol and an exfoliant. Psychophysiological electrodes will be attached, and impedance checks will be done on the EMG pairs. If impedance across each EMG pair is not below 5 KΩ, the cleaning and application procedure for that pair will be repeated. EKG electrodes will also be placed. All tasks involving psychophysiology will take place with the participant seated in a comfortable chair with a headrest, placed a pre-determined distance from the computer monitor. The IAPS, DIT, ABT, social touch, and social feedback tasks will be presented in a counterbalanced order. The psychophysiological equipment will then be disconnected. Participants will remain in the lab completing subjective measures of the drug effect every half-hour until at least 5:15pm (when we expect drug effects will end), or until

effects of the drug return to baseline (as measured by both subjective report and cardiovascular variables). Sessions will be separated by at least 72 hours.

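### The POMS Depression ANOVA, as most naturally read, makes the pre-dose score a fifth time level rather than a covariate and names no deciding term, so group x dose shows only 4/5 of the mean post-dose effect

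*Combined protocol and SAP*

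**What the plan says.** Under Data Analysis, subjective effects are tested by "three-way repeated measures analysis of variance (ANOVA", "with group (high vs. low BDI scores) as the between-group factor and dose and time as within-subjects factors". The same paragraph states: "Our primary mood measure will be scores on the Depression scale of the POMS". The hypothesis is that the drug will "reduce depressed mood in those individuals with high scores on the BDI", which is an interaction between BDI group and dose, possibly varying over time. The paragraph does not list the levels of time, gives the pre-dose score no role as covariate or change score, names no deciding term, and has no rule for a missing reading.

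The Timeline gives the pre-dose reading as "9:15am – Mood (POMS), drug effect (DEQ) and cardiovascular measures", with the tablet at 9:30. The same entry, "Mood (POMS), drug effect (DEQ) and cardiovascular measures", recurs at 10:00, 10:30, 12:30 and 1:00. The Procedure section runs on an afternoon clock but keeps the same spacing for the first readings, and it labels the pre-dose reading as the first time point: "We will then take Time 1 measures of subjective mood, drug effects and cardiovascular variables".

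The picture, attention, social feedback and touch outcomes get linear or generalized linear mixed models in lme4. Only the subjective measures get an ANOVA.

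**The concern.** A factor called time, a first reading called Time 1 and no other use for that reading point to a five-level factor. Two things follow.

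- Group x dose averages over all five levels, and at one of them no drug effect is possible.
- Group x dose x time does use the pre-dose level, as an implicit baseline, but spreads the signal over 4 degrees of freedom.

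Neither term uses the pre-dose score as a covariate to remove day-to-day variation in mood, although the score is collected at both sessions. Because no term is named as decisive, the choice could also be made after seeing the data, which gives two chances at significance. A null result on the main mood measure would be hard to interpret.

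**Working it through.** **Inputs from the documents.** There are two sessions per participant. Each has 1 pre-dose and 4 post-dose POMS readings (Timeline), so 10 readings per participant. The target is 86 completers, about half in each BDI range, so 43 vs 43. The same sentence gives 18 men and 18 women, which makes 36. The comparison barely depends on N: at 18 per group, group x dose power is the same to within a point.

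**The plan's own figure.** No power, alpha, effect size, SD or correlation is stated, so 86 cannot be reproduced. The consent target implies (120 - 86)/120 = 28.3% loss.

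**Assumptions.** Two-sided alpha is 0.05. Stable participant differences cancel in the crossover. The remaining within-person variance is set to 1 and split into a session part r and a residual part 1 - r. r runs from 0 to 0.7.

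**Variance of a participant's drug-minus-placebo difference, and effect shown** (d = mean post-dose group difference in drug effect):

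- Adjusted mean of four post-dose readings: variance 2(r + (1-r)/4 - r²), effect d.
- Group x dose over five levels: variance 2(r + (1-r)/5), effect (0 + 4d)/5 = 0.8d. This holds for any post-dose profile with mean d.
- Group x dose x time, constant effect: the squared deviations of (0, d, d, d, d) from their mean sum to 0.8d², and the error variance is 2(1-r).

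The non-centrality is the squared effect (for the three-way term, the sum of squared deviations) divided by variance x 2/43. Degrees of freedom are 1 and 83, 1 and 84, and 4 and 336.

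**Worked case, r = 0.5.** The adjusted contrast has 80% power at d = 0.529.

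- Adjusted: 0.2803 / (0.75 x 2/43) = 8.03, power 80%.
- Group x dose: (0.8 x 0.529)² = 0.1794, and 0.1794 / (1.2 x 2/43) = 3.21, power 43%.
- Three-way: 0.8 x 0.2803 = 0.2242, and 0.2242 / (1.0 x 2/43) = 4.82 on 4 df, power 38%.

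A simulation of 4,000 trials at r = 0.5 gave 79%, 41% and 37%.

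**Power when the adjusted contrast is fixed at 80%:**

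| r | group x dose, any profile | three-way, constant effect | three-way, build-up or peak | three-way, no effect at 30 min |
|---|---|---|---|---|
| 0 | 71% | 14% | 24-25% | 34% |
| 0.3 | 55% | 28% | 50-53% | 68% |
| 0.5 | 43% | 38% | 65-68% | 83% |
| 0.7 | 28% | 47% | 76-80% | 91% |

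The build-up and peak profiles are (0, 0.3, 0.6, 1, 1) and (0, 0.3, 1, 1, 0.5). The last column uses (0, 0, 1, 1, 1). The information in group x dose relative to the adjusted contrast is 0.64(r + (1-r)/4 - r²)/(r + (1-r)/5), which is 0.80, 0.56, 0.40 and 0.24 for the four rows.

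**Missing readings.** If each of ten readings is missing independently with probability q, a complete-case ANOVA loses a share 1 - (1-q)^10 of participants. That is 4.9% (about 4 of 86) at q = 0.5% and 18.3% (about 16 of 86) at q = 2%. Starting from 80% power at r = 0.5, this costs about 2 to 9 points.

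**The case against.** A reader might infer that the plan states that the pre-dose reading is a time level and that anyone with a missing form is removed. It states neither. The first is the natural reading of the schedule and the Time 1 label. The second is how a classical repeated-measures ANOVA behaves by default. Gaps should be few, because forms are completed in supervised sessions and the sample target counts completers: "to recruit 86 complete subjects we will need to consent 120 participants".

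A reader might also infer that much of the power is lost whatever happens. The documents do not support that, for three reasons.

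- **Profile.** The Drug and Doses section puts onset at 30 minutes, which is when the first post-dose POMS is taken, so a flat effect is doubtful. With nothing at that reading, the three-way test reaches 83% and 91% at r = 0.5 and 0.7 and beats the adjusted contrast, which itself averages in the 30-minute reading.
- **Meaning of r.** It is the session share of within-person variance, not the raw within-session correlation. If the raw correlation is 0.5 within sessions and 0.3 to 0.4 between them (assumed), r is (0.5 - 0.3)/(1 - 0.3) = 0.29 down to (0.5 - 0.4)/(1 - 0.4) = 0.17, and group x dose power is 56% to 63%.
- **Stakes.** This is the primary mood measure. None of the four aims is a mood outcome, and no power target is stated.

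All of this stands, and it limits the size of the claim. It does not remove the 4/5 dilution of group x dose, which holds at every profile, or the absence of a named deciding term.

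**Conclusion.** The point holds in conditional form. On the five-level reading, the dilution of group x dose to 4/5 is exact, and its power falls from 80% to between 71% and 28% over r = 0 to 0.7. Group x dose x time does worse than that at low r and can do better than the adjusted contrast when r is high and the effect builds up. The size of the loss therefore depends on r, on the time profile and on which term decides. The documents fix none of these. A general claim that the plan discards most of its power is not established. Loss through missing readings is a secondary matter. The change is still worth making, because it uses data already collected and replaces an open choice of term with one stated contrast.

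**What to change.** Analyse the post-dose POMS Depression readings in lme4, in line with the task outcomes:

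- **Fixed effects:** drug, the planned high/low BDI group, drug x group, time, drug x time, drug x group x time, and session.
- **Covariates:** that session's pre-dose POMS Depression score and the participant's mean pre-dose score.
- **Random intercepts:** participant and participant-by-session.
- **Deciding contrast:** drug x group averaged over the post-dose readings, named in advance as the only one.
- **Missing data:** keep participants with partial post-dose data, and state a rule for a missing pre-dose score, because lme4 omits rows with a missing covariate.

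The cost is analysis wording and slightly more analysis work, with no new data or procedures. The downside is some loss of power against the omnibus three-way test if the effect varies strongly over time. If the sponsor keeps the ANOVA, the plan should at least state the levels of time, the role of the pre-dose score, the deciding term and the handling of missing readings.

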In addition to the evidence implicating reduced endogenous opioid signaling in intensified responses to negative social input, studies in animals have shown that exogenously administered opiate agonists can have the opposite effect, reducing reactivity to such stimuli. It has been shown that opioid agonists reduce distress calls in response to social isolation in rodents (Panksepp, Najam, & Soares, 1979), chicks (Warnick, McCurdy, & Sufka, 2005), and non-human primates (Kalin, Shelton, & Barksdale, 1988). The “brain opioid hypothesis of social attachment” suggests that reduced opioid neurotransmission increases desire for attachment (Fabre-Nys, Meller, & Keverne, 1982), whereas increases in opioid signaling act as a proxy for social reward, thereby reducing the need for social interaction (Stein, van Honk, Ipser, Solms, & Panksepp, 2007; Herman & Panksepp, 1978; Panksepp et al., 1979). While there is a great deal of evidence in the animal literature that exogenous opiates act to blunt responses to negative social stimuli, this question has not been fully addressed in humans. An exception to this is one recent study, in which the investigators administered buprenorphine to healthy volunteers and found that the drug reduced participants’ ability to recognize fearful facial expressions (Ipser et al., 2013). Additionally, a handful of small studies have shown that buprenorphine is effective in treating treatment-resistant depression (Bodkin et al., 1995; Emrich et al., 1982; Nyhuis et al., 2008). In the study proposed here, we seek to determine the effect of an opioid agonist on a battery of tasks assessing an array of social behaviors in an effort to more thoroughly understand the role of opioids in mediating responses to social stimuli. Further, we plan to recruit subjects with a range of scores for depressed and anxious mood, in an effort to determine whether the drug is more effective in individuals scoring higher on this measure.

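### The only planned test of depressed mood as a moderator uses BDI-II as high vs low, with no cut stated; continuous BDI-II is a cheap improvement

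*Combined protocol and SAP*

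**What the plan says.** The Data Analysis section assesses subjective drug effects by a repeated measures ANOVA with three factors, "with group (high vs. low BDI scores) as the between-group factor and dose and time as within-subjects factors". On the outcome it says: "Our primary mood measure will be scores on the Depression scale of the POMS". The hypothesis attached to this analysis is: "We hypothesize buprenorphine will dose-dependently reduce depressed mood in those individuals with high scores on the BDI". The section does not say which score separates high from low, or which interaction tests the hypothesis.

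The Background states the recruitment aim: "we plan to recruit subjects with a range of scores for depressed and anxious mood". The reason given there is to see if people with higher scores benefit more from the drug. The Subjects paragraph under Methods lists the standard BDI-II severity categories, which separate mild (14–19) from moderate (20–28), and then says: "We will aim to recruit approximately half the participants in the 0–13 range, and half in the 14–28 range".

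The models under Behavioral Tasks (IAPS, ABT, social feedback and social touch) contain drug and, where relevant, stimulus type. None contains BDI-II. The two-level group factor is therefore the plan's only analysis of depressed mood as a moderator.

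**The concern.** The Background asks a graded question, and the trial collects a graded score to answer it. The analysis then reduces that score to two levels. If the cut is at 13/14, scores of 13 and 14 are placed on opposite sides, while 14 and 28 are treated as the same.

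Whether the drug works better at higher scores is a comparison between people: each person's drug-minus-placebo difference is set against that person's BDI-II. With 86 completers split about evenly, that is roughly 43 against 43. The documents show no power calculation, so no margin is known that could absorb a loss of information. After a null result, it would be hard to tell an absent moderation from one blurred by the coarse grouping.

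The missing cut-point adds a smaller problem. The 13/14 boundary can be inferred from the recruitment target, but the analysis text does not fix it. A split chosen after the data are seen, for example at the median, remains open.

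**Working it through.** **Plan's own figure.** There is none to reproduce. The documents give no alpha, sidedness, power, effect size or SD for this analysis, and no distribution of scores within the bands.

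**Inputs from the documents.** N = 86 completers; about half at BDI-II 0–13 and half at 14–28.

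**Assumptions made here.** Two-sided alpha 0.05; 80% power for the test on continuous BDI-II; one drug-minus-placebo summary of POMS Depression per person; that difference linear in BDI-II; a cut at 13/14; the within-band spreads listed below.

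**Formula.** Under linear moderation, the efficiency of the split relative to the continuous score is the squared correlation between BDI-II and the high/low indicator. With half the sample in each group this is

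efficiency = [(mean of high band − mean of low band) / 2]² / Var(BDI-II).

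**Even spread within each band (integer scores).**
- Band means: 6.5 and 21.0. Half the difference: 14.5 / 2 = 7.25. Squared: 52.56.
- Within-band variances: (14² − 1)/12 = 16.25 and (15² − 1)/12 = 18.67; average 17.46.
- Var(BDI-II) = 52.56 + 17.46 = 70.02.
- Efficiency = 52.56 / 70.02 = 0.751, a loss of 24.9%. Equivalent N = 86 × 0.751 = 64.6, so about 21 participants' worth of information is lost.

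**Power.** With 84 degrees of freedom, 80% power needs a noncentrality of 2.834. For the split this becomes 2.834 × √0.751 = 2.456, which gives 68%. If the BDI-II trend left inside each group is also counted as residual noise, the figure is 67%; a simulation of 20,000 trials gave 66% for the split against 79% for continuous BDI-II.

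**Other assumed spreads.**

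| Spread within bands | Efficiency | Loss | Equivalent N | Power (from 80%) |
|---|---|---|---|---|
| Falling from the bottom of each band, decay constant 2 points | 0.929 | 7.1% | 79.9 | 77.0% |
| Same, 3 points | 0.872 | 12.8% | 75.0 | 74.4% |
| Same, 4 points | 0.832 | 16.8% | 71.6 | 72.4% |
| Even | 0.751 | 24.9% | 64.6 | 68.0% |
| Low band even, high band falling (3 points) | 0.676 | 32.4% | 58.1 | 63.4% |
| Normal around 13.5, SD 5, within 0–28 | 0.647 | 35.3% | 55.6 | 61.5% |
| Normal, median split (2/π) | 0.637 | 36.3% | 54.7 | 60.9% |

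These are shapes that were tried, not bounds; tighter crowding at the cut would lose more.

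**Reverse case.** If the true effect is a step exactly at 14 and scores are evenly spread, simulation with the group test at 80% gives 67% for the linear BDI-II term.

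**The case against.** The strongest case for the plan is that a grouped analysis fits part of the design. Recruitment is in two bands that meet at a standard severity cutoff, and the hypothesis in Data Analysis concerns people with high scores, not a slope. The Background question can also be answered by comparing two groups. All of this stands, and it is why the banded comparison should be kept. It does not require the split to be the only analysis: recruiting in bands does not oblige one to analyse in bands, and an estimated drug effect at a high BDI-II value addresses the high-score hypothesis directly.

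The second objection is that the size of the loss depends on the assumed spread and on linearity, neither of which the documents give, and that under a step at 14 the advantage reverses. This also stands. The documents do not argue for a step, but nor do they argue for a line.

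A reader might infer more than the documents support:
- That a quarter of the information is lost as a matter of fact. It is one scenario in a wide range.
- That recruitment guarantees scores across 0–28. The plan only aims for about half in each band. It excludes Major Depressive Disorder and Axis I mood disorders, so the upper end may be thin.
- That the trial's primary endpoint is compromised. POMS Depression is called the primary mood measure; Aims 1–4 concern social stimuli, and their models have no BDI-II term.

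Finally, the sample size is itself unclear: "86 healthy volunteers (18 male, 18 female; age range 18-35 years) will participate in the experiment" gives sexes that sum to 36. The efficiency ratio does not depend on N, but the equivalent-N column and the power figures take 86 at face value.

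**Conclusion.** The point holds as a cheap improvement. BDI-II enters the plan's only moderation analysis as two groups with no stated cut, although the stated purpose is to learn whether higher scorers respond more. If the drug-placebo difference on POMS Depression is linear in BDI-II, the split costs about 25% of the information on the BDI-by-drug term under even spread, and about 7% to 36% under the other spreads tried. From an assumed 80% power at N = 86 and two-sided alpha 0.05, that means about 68% under even spread and roughly 61% to 77% across the range.

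The loss is confined to moderation. The drug-placebo comparison averaged over participants is made within persons and does not depend on how BDI-II is coded. The documents do not support reading this as an invalid analysis or as a flaw in the trial's main drug comparisons.

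**What to change.** In the POMS Depression model, replace the group factor with centred continuous BDI-II, keep dose and time, and name BDI-II by drug as the main moderation test. Check for non-linearity, for example with a quadratic or spline term. Report the estimated drug effect with its confidence interval at a low and a high score, such as 5 and 20, so that the high-score hypothesis gets a direct answer. Keep 0–13 vs 14–28 as a secondary analysis and for plots, with the 13/14 cut written into Data Analysis before unblinding.

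The cost is analysis wording only. BDI-II is already collected, and mixed models in lme4 are already planned for the behavioural tasks. The downside is the linearity assumption: if the effect is really a step at 14, the group test is the more powerful one (about 80% vs 67%). The non-linearity check and the secondary comparison would help to show this.
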